8.1.3.2. Planned Exploratory Efficacy Display Details

Hgb Variability

The number and percentage of subjects with a Hgb value < 7.5g/dL and the number of times a Hgb value < 7.5 g/dL occurs during the EP and the MP will be summarized by treatment group using central laboratory Hgb values and separately using HemoCue Hgb values. This summary will be presented using evaluable Hgb values only (see Section 10.6.3). The central laboratory summary will be considered the primary summary of this data.

The number and percentage of subjects with a >1 g/dL increase in Hgb over 2 weeks (assessed at Week 2 and Week 4) or a >2 g/dL increase in Hgb within any 4-week period from Week 4 to Week 52 will be summarized by visit and overall at Week 52 by treatment group using HemoCue Hgb values. This summary will be presented using evaluable Hgb values only (see Section 10.6.3).

The number and percentage of subjects with a >2 g/dL increase in Hgb within any 4week period from Week 4 to Week 52 will be summarized by visit and overall at Week 52 by treatment group using central laboratory Hgb values. This summary will be presented using evaluable Hgb values only (see Section 10.6.3). The central laboratory summary will be considered the primary summary of this data.

The number and percentage of subjects with a >1 g/dL decrease in Hgb over 2 weeks (assessed at Week 2 and Week 4) or a >2 g/dL increase in Hgb within any 4-week period from Week 4 to Week 52 will be summarized by visit and overall at Week 52 by treatment group using HemoCue Hgb values. This summary will be presented using evaluable Hgb values only (see Section 10.6.3).

The number and percentage of subjects with a >2 g/dL decrease in Hgb within any 4week period from Week 4 to Week 52 will be summarized by visit and overall at Week 52 by treatment group using central laboratory Hgb values. This summary will be presented using evaluable Hgb values only (see Section 10.6.3). The central laboratory summary will be considered the primary summary of this data.

The number and percentage of subjects with a Hgb value ≥ 12 g/dL and the number of times a Hgb value ≥ 12 g/dL occurs during the EP and the MP will be summarized by treatment group using central laboratory Hgb values and separately using HemoCue Hgb values. This summary will be presented using evaluable Hgb values only (see Section 10.6.3). The central laboratory summary will be considered the primary summary of this data.

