10.6.3. Efficacy

10.6.3.1. Hemoglobin Endpoints

Не	moglobin Values		
Ce	ntral Laboratory and HemoCue Hgb Values		
•	 When source of Hgb measurement is not specified: For reporting purposes, central laboratory Hgb values will be used, unless otherwise specified. However, if a central laboratory Hgb value is missing, a corresponding non-missing HemoCue Hgb value will be used. This approach will be used for the co-primary Hgb analysis. 		
•	Some displays may be created for either central laboratory Hgb values only or HemoCue Hgb values only. The central laboratory summary will be considered the primary summary in this case.		
Ev	aluable Hemoglobin Values		
•	Evaluable Hgb values are on-treatment Hgb values (see Section 10.4.1) that are not taken within the 8 weeks following a red blood cell transfusion, a whole blood transfusion, or a non- randomized ESA treatment which occurs on or after the randomization date. Red blood cell transfusions, whole blood transfusions and non-randomized ESA treatments occurring on or after the randomization date are identified by comparing the start and stop date of the respective transfusion or ESA concomitant medication record to the randomization date.		
Im	Imputed Hemoglobin Values		
•	For each missing value between baseline to Week 52 (inclusive), 200 imputed values will be generated using the multiple imputation method (see Section 7.1.2). The average of these 200 imputed values will be used as the value for this missing value in the summary tables and figures.		

He	emoglobin V	alues				
•	For co-primary efficacy Hgb analysis and the corresponding subgroup analyses using all available observed and imputed Hgb values (on and off-treatment), Rubin's rules [Rubin, 1987] will be used to combine results of the imputed datasets using SAS PROC MIANALYZE procedure.					
EF	[•] Hemoglobi	n Value for Co	p-primary Hg	b Analysis		
•	(See Section during this Should the	on 10.6.1) inclu time period. assessment da	ding any impu ates for Hgb v	uted and unsch alues from the	treatment) Hgb values neduled Hgb values that Early Treatment Disco	t were taken ntinuation visit
					e values will be include ot be included in the EF	
EF	-	-			ble Hgb Supportive Ar	

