10.6.4.3. Adverse Events

Adverse Events

AEs of Special Interest

Adverse events of special interest are classified as follows:

- Thrombosis and/or tissue ischemia secondary to excessive erythropoiesis
- Cardiomyopathy
- Pulmonary artery hypertension
- Cancer-related mortality and tumor progression and recurrence
- Esophageal and gastric erosions
- Proliferative retinopathy, macular edema, choroidal neovascularization
- Exacerbation of rheumatoid arthritis
- Worsening of hypertension

Potential AESIs will be identified through a pre-defined terms of interest process in which predefined lists of AE preferred terms corresponding with each AESI will be used to identify events considered to be potential AESIs. Sites will be prompted via query to complete any necessary additional information for these AESIs in the eCRF.

For the category of thrombosis and/or tissue ischemia secondary to excessive erythropoiesis, after the terms of interest list has been applied, the additional Hgb criteria described below will be applied to identify only those events that are considered to be secondary to excessive erythropoiesis as meeting the AESI definition for thrombosis and/or tissue ischemia secondary to excessive erythropoiesis.

Thrombosis and tissue ischemia events will be considered to be secondary to excessive erythropoiesis if during the window of [AE start date – 30 days, AE start date +15 days] any one of the following 3 events occurs:

- Any Hgb value \geq 13 g/dL (measured pre-dialysis)
- Hgb increase > 2 g/dL over 2 weeks (+1 week)
 - Note: for programming purposes, a +1 week window is applied, corresponding to the allowable visit window, to look for increases > 2 g/dL over 3 weeks
- Hgb increase > 4 g/dL over 4 weeks (+1 week)
 - Note: for programming purposes, a +1 week window is applied, corresponding to the allowable visit window, to look for increases > 4 g/dL over 5 weeks

To identify Hgb increases that meet the increase criterion above, all Hgb values taken within [AE start date – 58 days, AE start date + 15 days] will be identified. This corresponds to identifying Hgb

200807

Adverse Events

values that occurred 4 weeks before the [AE start date – 30 days, AE start date +15 days] window of interest. HemoCue Hgb and central laboratory Hgb values will then be evaluated separately to identify increases, so that HemoCue and central laboratory Hgb values are not compared to each other to identify an increase.

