For HemoCue Hgb and separately for central laboratory Hgb values, if there is a Hgb value (or daily Hgb average) within the [AE start date – 30 days, AE start date +15 days] window and an earlier Hgb value (or daily Hgb average) that is within the larger [AE start date – 58 days, AE start date + 15 days] window, and the amount of time between the two Hgb values is:

- Between 1 day and 3 weeks, inclusive, then the Hgb values will be compared to determine if there has been a Hgb increase > 2g/dL.
- Between 15 days and 5 weeks, inclusive, then the Hgb values will be compared to determine if there has been a Hgb increase > 4g/dL.

Unscheduled Hgb values will also be used in the assessment of secondary to excessive erythropoiesis following the guidance specified in Section 10.6.3 for unscheduled Hgb values and multiple Hgb values on the same date.

Pre-defined Lists of AE Preferred Terms Corresponding with Each AESI

Thrombosis and/or tissue ischemia secondary to excessive erythropoiesis

- Narrow SMQ: Embolic and thrombotic events, arterial
- Narrow SMQ: Embolic and thrombotic events, venous
- Narrow SMQ: Embolic and thrombotic events, vessel type unspecified and mixed arterial and venous
- Broad SMQ: Thrombophlebitis
- Additional Preferred Terms:
 - Vascular access site occlusion
 - Vascular access site complication
 - Retinal vascular occlusion
 - Administration site ischaemia
 - Anterior segment ischaemia
 - Application site ischaemia
 - Biliary ischaemia
 - Bone marrow ischaemia
 - Brain stem ischaemia
 - Catheter site ischaemia
 - Cerebellar ischaemia
 - Cerebral ischaemia
 - ECG signs of myocardial ischaemia
 - Gastrointestinal ischaemia
 - o Graft ischaemia
 - Hepatic ischaemia

- Stoma site ischaemia
- o Subendocardial ischaemia
- o Uterine ischaemia
- o Vaccination site ischaemia
- o Vestibular ischaemia
- o Cerebral small vessel ischaemic disease
- o Colitis ischaemic
- o Delayed ischaemic neurological deficit
- Hypoxic-ischeaemic encephalopathy
- Ischaemic cardiomyopathy
- Ischaemic cerebral infarction
- Ischaemic contracture of the left ventricle
- o Ischaemic enteritis
- o Ischaemic gastritis
- Ischaemic heart disease prophylaxis
- Ischaemic hepatitis

0

0

0

0

0

0

0

0

0

0

200807

Adverse	Events

- Implant site ischaemia 0
 - Infusion site ischaemia 0
 - Injection site ischaemia 0
 - Intestinal ischaemia 0
 - Ischaemia 0
 - Macular ischaemia
 - Medical device site ischaemia
 - Myocardial ischaemia 0
 - Peripheral ischaemia 0

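### The Hgb-rise criteria for thrombosis or ischemia secondary to excessive erythropoiesis have no transfusion exclusion, so a rise from donor blood, even blood given after the event, can earn the label

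*SAP*

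**What the plan says.** Section 10.6.4.3 first finds candidate events by preferred term. It then applies Hgb criteria whose stated purpose is to keep only events secondary to excessive erythropoiesis: "Thrombosis and tissue ischemia events will be considered to be secondary to excessive erythropoiesis if during the window of" 30 days before to 15 days after AE start (in the SAP's notation, "AE start date – 30 days, AE start date +15 days") any one of three things happens. These are Hgb of at least 13 g/dL, a rise above 2 g/dL over 2 weeks (+1 week), or a rise above 4 g/dL over 4 weeks (+1 week).

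For the rises, "all Hgb values taken within [AE start date – 58 days, AE start date + 15 days] will be identified". For the first rise criterion the spacing is "Between 1 day and 3 weeks, inclusive, then the Hgb values will be compared"; for the second, "Between 15 days and 5 weeks, inclusive, then the Hgb values will be compared". HemoCue and central laboratory values are assessed separately. "Unscheduled Hgb values will also be used in the assessment of secondary to excessive erythropoiesis", with a pointer to Section 10.6.3 for unscheduled and same-date values only.

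Elsewhere the SAP treats transfusion as distorting Hgb. Evaluable values (10.6.3.1) leave out those taken "within the 8 weeks following a red blood cell transfusion, a whole blood transfusion" or a non-randomized ESA. The displays of rapid Hgb rise in 8.1.3.2 carry the statement "This summary will be presented using evaluable Hgb values only", and the clopidogrel displays of Hgb rise in 8.2.9 do the same. The principal secondary IV iron analysis (8.1.1.2) stops at the first transfusion.

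**The concern.** A rise produced by donor red cells is not erythropoiesis, and a transfusion given after onset cannot have contributed to the event. The rise criteria nonetheless count both. They set no minimum Hgb, so a subject who stays below the 10-11 g/dL target throughout can be labelled as having excessive erythropoiesis. The one rule that gives a rise a causal name lacks the safeguard used in the purely descriptive displays of Hgb rise.

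At stake is the meaning of a Tier 1 AESI. Section 8.2.4 compares it between arms by a CMH test at an unadjusted two-sided 0.05, and 8.2.4.2 adds rates, relative risk and possibly cumulative incidence plots. Transfusion is itself a post-randomization outcome, summarized by arm in 8.1.3.2. Randomization therefore does not guarantee that false labels balance.

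**Working it through.** The plan gives no figure to reproduce, so the check is to write the rule as stated and run it on constructed series.

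**Rule.** Let days be counted from AE start. Take two values from the same source, h1 on day d1 and h2 on day d2, with d1 at or after day -58, d2 later than d1, and d2 between -30 and +15. The event is labelled if
- h2 - h1 > 2 and 1 ≤ d2 - d1 ≤ 21, or
- h2 - h1 > 4 and 15 ≤ d2 - d1 ≤ 35, or
- any value from day -30 to +15 is at least 13 g/dL.

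**Series.** Hgb values and transfusion days are assumed for illustration. In A and B an earlier value of 8.0 on day -28 was also included; it triggers nothing.

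| Series | Values (day: g/dL) | Transfusion | Rise and gap | Rule as written | With 8-week exclusion | Values up to onset only | Pairs spanning a transfusion dropped |
|---|---|---|---|---|---|---|---|
| A | -2: 7.0; +5: 9.2 | day +1 | 2.2 in 7 days | labelled | not labelled | not labelled | not labelled |
| B | -12: 6.8; -5: 9.0 | day -10 | 2.2 in 7 days | labelled | not labelled | labelled | not labelled |
| C | -28: 9.5; 0: 10.5 | none | 1.0 in 28 days | not labelled | not labelled | not labelled | not labelled |
| D | -2: 7.0; +5: 8.9 | day +1 | 1.9 in 7 days | not labelled | not labelled | not labelled | not labelled |
| E | -25: 8.0; -8: 10.5 | day -35 | 2.5 in 17 days | labelled | not labelled | labelled | labelled |

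**Reading.**
- A and B show the defect. Hgb never exceeds 9.2 g/dL, yet the label is given. In A the transfusion follows the event.
- Cutting values off at onset cures A but not B, so the +15-day limit is not the whole problem.
- D shows that transfusion alone is not enough; a threshold must be crossed.
- E is a rise with no transfusion between the two values. The 8-week exclusion discards it, because -35 + 56 = +21, past the end of the window. More generally, -41 + 56 = +15, so a transfusion on any day from -41 to -31 removes every later value in the classification window and neither rise criterion can be met.

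**How often could a qualifying pair arise?** By the schedule in 10.2.1, visits from Week 4 to Week 52 are 4 weeks apart, mostly with a window of ±1 week. Adjacent scheduled values are nominally 28 days apart and at the closest 28 - 14 = 14. A gap of 21 days or less therefore needs at least 7 days of drift, or an unscheduled sample. Only the HemoCue values at Day 1, Week 2 and Week 4 are planned closer together. After Week 52 visits are 12 weeks apart: 84 - 14 = 70 days exceeds both 21 and 35, so a pair must include a sample off that schedule. A 28-day pair can meet the second criterion, but only with a rise above 4 g/dL.

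**The case against.** The strongest reply is that the error is rare and its consequence small. Both values must come from the same source, HemoCue or central laboratory, and the rule names no local hospital results. Pairs within 21 days are uncommon on the 4-weekly and then 12-weekly schedule. The test is nominal only. Adjudicated MACE and the adjudicated thromboembolic composite do not use the label, treatment-emergent AEs are tabulated by preferred term whatever the label, and transfusions are summarized by arm. All of this stands, and it limits the point. It does not make the label right in the cases that do occur. Those tables also do not show which AESIs rested on a transfused pair.

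A second reply is that the rule is meant to be sensitive. The section's stated aim of keeping only events secondary to excessive erythropoiesis points the other way, and a supportive row preserves the sensitive count.

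A third is that part of the unscheduled-value entry in 10.6.3.1 is not legible in the copy reviewed. Its heading concerns unscheduled and same-date values, and nothing legible there excludes values after transfusion.

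It is also tempting to say that the evaluable-Hgb flag should simply be reused. Series E shows why not: it would discard rises unrelated to transfusion. It would also drop rises after non-randomized ESA, which are erythropoiesis.

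**Conclusion.** The rule as written can label an event as secondary to excessive erythropoiesis when the Hgb rise came from a transfusion, including one given afterwards. This is inconsistent with the SAP's other displays of Hgb rise. The conclusion follows from the text and needs no assumption about frequency; the series above only illustrate it.

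Three stronger readings are not supported:
- **That ischemic events in transfused, anemic subjects are labelled as a rule.** Only those with two same-source values spanning the transfusion and crossing a threshold are.
- **That false labels are a large share of the AESI count.** If 5-15% of such events had a transfusion between two values, half of those rose above 2 g/dL and 10% truly met the rule, the share would be 2.5/12.5 = 20% to 7.5/17.5 = 43%. None of those inputs is in the SAP, so the range is no estimate.
- **That one arm is favored.** The SAP gives no transfusion rates, so neither the direction nor the size of any between-arm bias can be stated.

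The effect is confined to one nominal Tier 1 comparison and its displays. The co-primary endpoints are untouched.

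**What to change.** Add one sentence to 10.6.4.3: for the two rise criteria only, disregard any pair of Hgb values with an RBC or whole blood transfusion dated on or after the earlier value and on or before the later value. Use all recorded transfusion dates, not only the on-treatment transfusions counted in 10.6.3.4, because a transfusion after the event may fall after treatment has stopped.

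Leave the criterion of at least 13 g/dL unchanged. Do not exclude values after ESA use, and do not apply the blanket 8-week exclusion. Report the unrestricted count as a supportive row beside the restricted one.

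The cost is one sentence, a date comparison on data already collected, and one table row. The downside is small: a true drug-driven rise in a pair that also spans a transfusion leaves the restricted count, but stays visible in the supportive row.

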10.6.4.5. Vital Signs

Vi	Vital Signs	
Pr	e- and Post- Dialysis HR & Weight	
•	For subjects undergoing dialysis in-clinic, both pre- and post- dialysis HR & weight values will be measured.	
•	Unless otherwise specified, for summaries of HR & weight values, the post-dialysis HR & weight values for subjects undergoing dialysis in-clinic will be used.	
• If there is more than one vital sign value on the same date for the same vital sign value, then the vital sign values associated with scheduled visits will be used.		
•	If there are multiple values from a scheduled visit on the same date, then the average of the scheduled values will be used.	
•	 For purposes of flagging worst-case post baseline vital sign values: If there are multiple scheduled values on the same day, or only multiple unscheduled values on the same day, then the average of the values on that day should be used for the purpose of determining the worst-case value. 	

200807

• The EQ-5D-5L is a self-assessment questionnaire, consisting of five items covering five dimensions (mobility, self-care, usual activities, pain/discomfort, and anxiety/depression). Each dimension is measured by a five-point Likert scale (no problems, slight problems, moderate problems, severe problems, and extreme problems).

200807

EQ-5D-5L	
General	
 The responses for the five dimensions together form a five-figure description of a health state (i.e., the score of 11112 describes the health state of no problems with mobility, self-care, usual activities or pain/discomfort, but slight problems with anxiety/depression). EQ-5D-5L health states are converted to a single summary index score by applying a country-specific value set formula that essentially attaches weights to each of the levels in each dimension. The EuroQol Group's United Kingdom (UK) crosswalk value set for the health states will be used for all subjects, regardless of country. The converted single index using this value set will be on a scale from -0.594 to 1, where -0.594 is the country and 1 is the country. 	

• The EQ-5D-5L will only be assessed in the countries listed in Section 10.9.

General

- The EQ-VAS is a self-assessment visual analogue scale, ranging from 0=cci 100=cci
- The EQ-VAS will only be assessed in the countries listed in Section 10.9.

PGI-S

General

- The PGI-S is a 1-item questionnaire designed to assess a subject's impression of disease severity on a 5-point disease severity scale (absent, mild, moderate, severe, or very severe).
- Scores range from ^{CCI} as follows:

0	CCI
0	
0	
0	
0	

PGI-C

General

- The PGI-C is a 1-item questionnaire designed to assess a subject's impression of change in their anemia of CKD on a 7-point Likert-type response scale (very much improved, moderately improved, minimally improved, no change, minimally worse, moderately worse, or very much worse).
- Scores range from to as follows:

0	CCI - This section contained
0	Clinical Outcome Assessment data collection guestionnaires or
0	indices, which are protected by
0	third party copyright laws and therefore have been excluded.
0	
0	
0	

200807

10.7. Appendix 7: Premature Withdrawals & Handling of Missing Data

10.7.1. Premature Withdrawals

Element	Reporting Detail
General	 Subject study completion (i.e. as specified in the protocol) was defined as completing all phases of the study including the End of Study visit, with the following exception: subjects who die while on study are also considered as having completed the study. Withdrawn subjects will not be replaced in the study. All available data from subjects who were withdrawn from the study will be listed and all available planned data will be included in summary tables and figures, unless otherwise specified. Per protocol, subjects may prematurely discontinue study drug but are encouraged to remain in the study.

10.7.2. Handling of Missing Data

Element	Reporting Detail
General	 Missing data occurs when any requested data is not provided, leading to blank fields on the collection instrument: These data will be indicated by the use of a "blank" in subject listing displays, unless all data for a specific visit are missing in which case the data is excluded from the table. Answers such as "Not applicable" and "Not evaluable" are not considered to
	be missing data and should be displayed as such.
Outliers	 Any subjects excluded from the summaries and/or statistical analyses will be documented along with the reason for exclusion in the clinical study report.

10.7.2.1. Handling of Missing and Partial Dates

Element	Reporting Detail				
General	Partial dates will be displayed as captured in subject listing displays.				
Concomitant Medications	 Partial dates for any concomitant medications recorded in the CRF will be imputed using the following convention: 				
	 If the partial date is a start date, a '01' will be used for the day and 'Jan' will be used for the month 				
	 If the partial date is a stop date, a '28/29/30/31' will be used for the day (dependent on the month and year) and 'Dec' will be used for the month. 				
	 The recorded partial date will be displayed in listings. 				
Adverse Events	• The eCRF allows for the possibility of partial dates (i.e., only month and year or only year) to be recorded for AE start/worsening and end dates. In such a case, the following conventions will be applied for calculating the time to onset and the duration of the event:				

Element	Reporting Detail				
	 Imputing a Start/Worsening Date from a Partial Start/Worsening Date: 				
	 If an imputed worsening date is before the start date, then the start 				
	date will be used as the imputed worsening date.				
	 Completely missing stop date: 				
	If only the day is missing, the first of the month will be used				
	unless the Screen Week -8 visit date, Run-In visit date or				
	treatment start date also occurs in the same month.				
	 If the treatment start date occurs in the same month, then the treatment start date will be used as the start/worsening date. 				
	Otherwise, if the Run-In visit date occurs in the				
	same month (and the treatment start date is not in that month), then the Run-In visit date will be used as the start/worsening date.				
	• Otherwise, if the Screen Week -8 visit date occurs in the same month (and the treatment start and Run-In visit dates are not in that month), then the Screen Week -8 visit date will be used as the				
	start/worsening date.				
	If the day and month are missing, then '01' will be used for the day and 'Jan' will be used for the month unless the Screen Week -8 visit date, Run-In visit date or treatment start date also occurs in the same year.				
	 If the treatment start date occurs in the same year, then the treatment start date will be used as the start/worsening date. 				
	 Otherwise, if the Run-In visit date occurs in the same year (and the treatment start date is not in that year), then the Run-In visit date will be used as the start/worsening date. 				
	 Otherwise, if the Screen Week -8 visit date occurs in the same year (and the treatment start and Run- In visit dates are not in that year), then the Screen Week -8 visit date will be used as the start/worsening date. 				
	 Partial or non-missing stop date is before the Run-in visit date: 				
	If only the day is missing, the first of the month will be used unless the Screen Week -8 visit date also occurs in the same month; in this case the Screen Week -8 visit date will be used as the start/worsening date.				
	If the day and month are missing, then '01' will be used for the day and 'Jan' will be used for the month unless the Screen Week -8 visit date also occurs in the same year; in this case the Screen Week -8 visit date will be used as the start/worsening date.				

Element	Reporting Detail					
_	• Partial or non-missing stop date is before treatment start date, and					
	either on or after Run-In date or has the same year (or year and					
	month) as the Run-In date:					
	> If only the day is missing, then the first of the month will be					
	used unless the Run-In Visit date also occurs in the same					
	month; in this case the Run-In Visit date will be used as the					
	start/worsening date.					
	➢ If the day and month are missing, then '01' will be used for					
	the day and 'Jan' will be used for the month unless the					
	Run-In Visit date also occurs in the same year; in this case					
	the Run-In Visit date will be used as the start/worsening					
	date.					
	 Stop date is partial with the same year (or year and month) as the 					
	treatment start date or is on or after the treatment start date:					
	\rightarrow If only the day is missing, then the first of the month will be					
	used unless the start date of study treatment also occurs in					
	the same month; in this case the study treatment start date					
	will be used as the start/worsening date.					
	 If the day and month are missing, then '01' will be used for 					
	the day and 'Jan' will be used for the month unless the start date of study treatment occurs in the same year; in					
	start date of study treatment occurs in the same year; in this case the study treatment start date will be used as the					
	start/worsening date.					
	 Imputing a Stop Date from a Partial Stop Date: 					
	 Latest of (start date and latest worsening date) is on or before the 					
	treatment stop date or is partial with the same year (or year and					
	month) as the treatment stop date:					
	If only the day is missing, the last day of the month will be					
	used unless the treatment stop date also occurs in the					
	same month; in this case the treatment stop date will be					
	used at the stop date.					
	 If the day and month are missing, then '31' will be used for 					
	the day and 'Dec' will be used for the month, unless the					
	stop date of study treatment also occurs in the same year;					
	in this case the study treatment stop date will be used as					
	the stop date.					
	 Latest of (start date and latest worsening date) is partial or non- 					
	missing and is after treatment stop date:					
	If only the day is missing, the last day of the month will be					
	used unless the study conclusion date also occurs in the					
	same month; in this case, the study conclusion date will be					
	used as the stop date.					
	 If the day and month are missing, then '31' will be used for 					
	the day and 'Dec' will be used for the month, unless the					
	study conclusion date also occurs in the same year; in this					
	case, the study conclusion date will be used as the stop					

Element	Reporting Detail				
	date.				
	• Completely missing start, worsening or end dates will remain missing, with no imputation applied. Consequently, time to onset and duration of such events will be missing.				
CV Safety Endpoint Events	Discussed in Section 10.6.4				

200807

